Participants at the Patient and Family Research Council felt strongly that *"all of these are important outcomes."* [name], Parent Partner, re-iterated this point: *"the developmental outcome matters only in the context of epilepsy and quality of life outcomes; they are all related and all important."*

Data Analysis [IR-3]. The centers from the *Neonatal Seizure Registry* enrolled 306 consecutive newborns with seizures due to acute symptomatic cause, and who survived hospital discharge, over our initial 12-27 months of collaboration (variable timing of initiation of enrollment by site). We conservatively estimate that we can enroll 150 of these infants to collect personal health information and follow up data, as well as 150 additional newborns over the 18 months proposed, for a total of 300 subjects with outcome measures for all three aims. This will require that we enroll ~50% of eligible newborns, a very achievable recruitment goal for an observational study.

Sample Size Calculations

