Aim 1a: Our hypothesis is that short duration treatment with phenobarbital will be inferior to long duration by no more than a non-inferiority margin of 7% in our primary outcome (functional developmental outcome, measured by the WIDEA FS) adjusted for propensity for maintenance of phenobarbital. This margin is well below the clinically-significant threshold since a developmental delay of more than 33% is needed before a child may access developmental services 26. If there is truly no difference in neurodevelopmental outcome among children who had short versus prolonged treatment with phenobarbital (Aim 1a), and using a 12 month WIDEA FS mean of 109 with standard deviation of 16.5 (Appendix 3), we calculate that 192 subjects are required to be 80% sure that the lower limit of a one-sided 95% confidence interval will be above the noninferiority limit of -7. The WIDEA (our primary outcome measure) is also validated for age 24-months. At age 24-months, the standard deviation of the WIDEA is lower than at 12 months, which will improve our power to detect differences between the groups and, using a similar sample size, lower our non-inferiority margin from 7% to 4.25% for the primary outcome while also increasing accountability for loss to follow-up from 15 to 20%. . Therefore our proposed N=300 newborns, divided into N1 (short duration: phenobarbital discontinued prior to discharge) = 90, and N2 (prolonged duration: phenobarbital continued at discharge) = 210, allows us to take into account loss to follow-up (conservatively estimated at 15%) and propensity score adjustment analysis to address causal inference (as discussed below), which requires that we inflate the sample size by 9%²⁸. Aim 1b: We hypothesize that there is no clinically significant difference in epilepsy frequency between the groups. If there is truly no difference between short versus prolonged treatment, with epilepsy incidence conservatively estimated at 20%²⁷, then we will have sufficient subjects to be 80% sure that the upper limit of a one-sided 95% confidence interval (or equivalently a 90% two-sided confidence interval) will exclude a difference of more than 13% between groups²⁹. The clinical importance of a potential difference of 13% in epilepsy incidence between the groups depends, according to our stakeholders and parent partners, on the results of the primary neurodevelopmental outcome analysis. If developmental outcomes are not different between the short- and prolonged- treatment groups, then a difference of 13% in epilepsy incidence is meaningful and parents would be willing to accept prolonged medication treatment in hopes of reducing the risk for epilepsy. If developmental outcomes are disparate between the two groups, then parents say that the epilepsy risk is less important and they would prefer the treatment regimen that is least likely to produce developmental disabilities.

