	Home on phenobarbital N= 30	Home off phenobarbital N=9	Unadjusted Relative Risk (95% Cl)	P-Value
Abnormal examination	10 (33.3 %)	6 (66.6 %)	0.7 (0.5-1.1)	0.07
Abnormal development	12 (40.0 %)	3 (33.3 %)	1.1 (0.8-1.5)	0.7
Epilepsy (any type)	6 (20.0 %)	0 (0.0 %)	1.3 (1.1-1.6)	0.2
Infantile Spasms	2 (6.7 %)	0 (0.0 %)	1.3 (1.1-1.6)	0.4

Table 2: Outcomes of children with neonatal seizures who were evaluated in clinical follow-up at age >6 months.

Statistical analysis and addressing causal inference [CI-1 to 6]. We will follow PCORI guidelines for addressing causal inference using *propensity score adjustment* as a strategy for addressing confounding by indication for Aims 1a and 1b^{22,23}. Using propensity scores, we will estimate the unbiased effect of short *versus* prolonged treatment with phenobarbital by accounting for all covariates that predict treatment duration.

Guillet, *et al*, examined duration of neonatal seizure treatment by surveying neonatologists and neurologists across the United States. They concluded that "*the coefficients of variation… were >0.2, which supports the notion that there is wide variability in thinking about actual practices*⁵," however no measured variables (including work setting, training, or geographic location) could account for the inconsistencies. Preliminary, unpublished data from the *Neonatal Seizure Registry* also suggest sufficient heterogeneity within our established group to adequately address the primary hypothesis using propensity scores. Although the centers care for similar patient populations (for example the primary cause of seizures at all centers is hypoxicischemic encephalopathy) and have similar initial management strategies (phenobarbital is, by far, the most common initial medication in all centers), management decisions regarding whether or not to maintain seizure medication until the time of outpatient follow-up are very discrepant. Among newborns enrolled in the *Neonatal Seizure Registry*, 23% had medication discontinued prior to discharge (range by site 3-75%), while 77% continued on anticonvulsants. Phenobarbital was the most commonly prescribed anticonvulsant (prescribed to 89% of those maintained on medication).

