Based on audits of our *Registry* data, we expect <1% missing data for the following key elements: institution, sex, ethnicity, gestational age at birth, delivery mode, Apgar scores, hypothermia treatment, indication for EEG, seizure type, primary seizure etiology, disposition and seizure medication prescribed at the time of discharge. For Aims 1 and 3, in our study design we have conservatively accounted for 15% loss to follow-up (the anticipated main source of missing data) and have adjusted our enrollment target accordingly. We will perform sensitivity analyses to assess the potential impact of loss to follow-up: we have extensive information about our participants and will compare those that are and are not lost to follow-up. We will compare our primary analysis (a complete case analysis) with an analysis using multiple imputation using the "multiple imputation with chained equations" methodology. This approach allows us to specify realistic models for each variable, such as the ordered categorical for the Engel scale. For Aim 2, we expect little to no missing data. Also, for Aim 3, we will audit the amount of missing data for the open-ended free-text questions to determine if there are patterns and will consult with our Parent Partners about ways to improve response rates if needed.

Heterogeneity of treatment effects [HT-1 to 4]. As suggested by PCORI methodological guidelines, all assessments of heterogeneity of the effect of short versus prolonged phenobarbital treatment have been preplanned and have been justified (see *Potential participant subgroups* section below). Analysis will be by entering subgroup by intervention interaction effects in the analyses described above to test for moderation.

Reporting plan [IR-6]. Data will be reported according to STROBE (Strengthening the Reporting of Observational studies in Epidemiology) guidelines, as is recommended for observational studies.

Patient-centered outcomes research (PCOR) data registry details are presented in Appendix 6.

D. Project Milestones and Timeline

Table 3: Project Timeline

	Months					
	1-6	7-12	13-18	19-24	25-30	31-36
Planning						
- Finalize protocol	\checkmark					
- IRB approval	\checkmark					
 Clinicaltrials.gov registration & results reporting 	~					\checkmark
Patient Enrollment						
- Start recruitment		\checkmark				
- Complete 25% recruitment		\checkmark				
- Complete 50% recruitment			✓			
- Complete 75% recruitment			✓			
- Complete enrollment				~		

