Appendix 6: Standards for Data Registries [DR-1 to DR-3]

Patient Follow-up will be at pre-specified ages as outlined in the proposal. The initial follow-up (2-4 month EEG) will be arranged at the time of enrollment for the N=150 prospectively enrolled infants. The Aim1 12-month, 18-month, and 24-month follow-up assessments for all participants will be conducted by telephone and will include:

- WIDEA FS (functional neurodevelopmental outcome, which is the primary endpoint, Appendix 3)
- Epilepsy assessment (Appendix 4)

As requested by our Parent Partner Advisory Panel, participating families may complete 12-month follow-up family wellbeing assessment for Aim 3 either by mail (paper copies of the questionnaires) or via online questionnaire administration (**Appendix 5**).

The 24-month contact is planned to be the last contact with patients and their families.

Adequacy of Follow-Up Duration: 24-month follow-up is both scientifically justified and practical. By 12 months, those with significant developmental delays can be identified using standard neurodevelopmental assessment instruments, such as the WIDEA FS. Additionally, those with the most severe forms of post-neonatal epilepsy, such as infantile spasms, typically present before the child's first birthday. Although more subtle developmental differences may emerge later, in school age children, longer follow-up is not feasible within a 3-year grant cycle. We plan to request permission from enrolled families to contact them at a later date for long-term outcome assessment, once additional funding is secured.

Retention and Expected Loss to Follow-Up: We anticipate excellent retention, since all neonates enrolled in this study will have close clinical follow-up with the study centers through a high-risk developmental follow-up program, pediatric neurology, and/or pediatric epilepsy. We have designed the protocol to avoid unnecessary travel to the study centers. The follow-up EEG will be recorded between ages 2 and 4 months, a timeframe during which typical neurology clinical assessments are scheduled. The assessments will be conducted via telephone interview (Aim 1), and online or by mail (Aim 3), rather than in-person evaluations. Despite this, we have accounted for a 15% loss to follow-up in our analysis plan.

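### Aim 1b claims 80% power to exclude a 13-point epilepsy difference without giving its basis; on the plan's own split, loss and inflation the power is about 74%

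*Combined protocol and SAP*

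**What the plan says.** Under Sample Size Calculations, the Aim 1b text assumes no true difference, with "epilepsy incidence conservatively estimated at 20" percent. It says there are enough subjects to be 80% sure that the upper limit of a one-sided 95% interval "will exclude a difference of more than 13% between groups". It attaches no evaluable number, allocation or loss rate to that statement.

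The surrounding text supplies those elements:

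- **Allocation.** The Aim 1a paragraph divides the 300 newborns into "N1 (short duration: phenobarbital discontinued prior to discharge) = 90, and N2 (prolonged duration: phenobarbital continued at discharge) = 210".
- **Propensity inflation.** The same paragraph says the propensity analysis "requires that we inflate the sample size by 9" percent. The section on statistical analysis and causal inference describes propensity adjustment "as a strategy for addressing confounding by indication for Aims 1a and 1b".
- **Loss.** The Missing data section says: "For Aims 1 and 3, in our study design we have conservatively accounted for 15% loss to follow-up". Appendix 6, on retention, repeats that "we have accounted for a 15% loss to follow-up in our analysis plan".

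Some text points towards less loss for epilepsy. The Data Analysis section speaks of enrolling "for a total of 300 subjects with outcome measures for all three aims". Table 1 and the epilepsy outcome description include medical record review. Appendix 6, on differential loss, expects an epilepsy diagnosis to be visible in the electronic record when a family cannot be reached.

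**The concern.** A reader who takes the 80% at face value and applies the plan's own allocation, loss and inflation cannot recover it. The figure matters because 13 points is the only epilepsy difference the plan names, and the decision rule in the statistical analysis section judges epilepsy rates against a non-inferiority limit. The Aim 1b text also reports that parents and stakeholders would regard a 13-point difference as meaningful if development does not differ, which is the hypothesised case. If power is lower than stated, an inconclusive epilepsy result is more likely than readers are told. With no basis shown, they cannot tell whether the 80% rests on equal groups, on near-complete chart ascertainment, or on deductions left out.

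**Working it through.** **Inputs.** Incidence p = 0.20 in both groups, true difference 0, one-sided 95% limit, margin 0.13 and target power 80% (Aim 1b); 300 split 90:210 and 9% inflation (Aim 1a); 15% loss for Aim 1 (Missing data section). Carrying the 9% to Aim 1b is a step taken here, because propensity adjustment is planned for that aim and no other inflation is given.

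**Formulas** (normal approximation, unpooled):

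- SE = √[p(1−p)(1/n1 + 1/n2)]
- Power = Φ(0.13/SE − 1.645)
- Difference excludable with 80% power = (1.645 + 0.842) × SE
- Effective N = 300 × (1 − loss) / inflation, split 30:70

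**Reproducing the stated figure.** With 117:117, SE = √[0.16 × (2/117)] = 0.0523. Then 0.13/0.0523 = 2.486, power = Φ(0.841) = 80.0%, and the excludable difference is 2.487 × 0.0523 = 13.0 points. The total of 234 equals the effective N found next, so the stated figure matches those subjects divided equally. The documents show no calculation, so this is an inference about its source.

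**The plan's own split and deductions.** Effective N = 300 × 0.85 / 1.09 = 233.9, or 70.2 and 163.8. SE = √[0.16 × (1/70.2 + 1/163.8)] = 0.0571. Then 0.13/0.0571 = 2.278, power = Φ(0.633) = 73.7%, and the excludable difference is 2.487 × 0.0571 = 14.2 points. Exact binomial enumeration of the Wald limit at 70:164 gives 72.5%.

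**Sensitivity to loss and inflation** (20% incidence, 30:70 split):

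| Loss | Inflation | Effective N | Power for 13 points | Excludable at 80% power |
|---|---|---|---|---|
| 20% | 9% | 220 | 71.4% | 14.6 |
| 15% | 9% | 234 | 73.7% | 14.2 |
| 10% | 9% | 248 | 75.8% | 13.8 |
| 5% | 9% | 261 | 77.7% | 13.4 |
| 0% | 9% | 275 | 79.6% | 13.1 |
| 15% | none | 255 | 76.8% | 13.6 |
| 0% | none | 300 | 82.5% | 12.5 |

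The 20% row is included because the Aim 1a paragraph mentions that loss allowance for the 24-month WIDEA.

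**Sensitivity to incidence** (both deductions, 70:164). The pilot in Table 2 had 6/30 and 0/9 with epilepsy, or 6/39 = 15.4%. Power for 13 points is about 81% at 15.4%, 74% at 20%, and 68% at an assumed 25%.

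**Cross-check with the other aims** (two-sided 5%, 80% power):

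- Aim 2: (1.960 + 0.842) × 0.71 × √(1/70.2 + 1/163.8) = 0.284, matching the stated 0.28. The full 90:210 gives 0.251.
- Aim 3: the text uses 36:84, a 30:70 split after dropout. (1.960 + 0.842) × √(1/36 + 1/84) = 0.558, matching the stated 0.56.

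The figures for both aims fit a 30:70 split of a reduced sample. The Aim 1b figure does not.

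**The case against.** The strongest reply is that no arithmetic error is shown. The sentence claims only enough subjects for 80%, and all 300 at 90:210 give 82.5% (81.0% by exact enumeration). With the inflation and no loss the result is 79.6%, the stated figure to rounding. Loss is also least certain for this outcome, because record review is part of the epilepsy assessment and is offered as the fallback when a family cannot be reached. The 9% is stated in the Aim 1a paragraph, for a continuous outcome.

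Part of this stands. The documents do not prove how the figure was obtained, and the 74% depends on applying both deductions. But the 82.5% reading ignores a loss that the plan charges to Aim 1 without exempting epilepsy, and an adjustment that it applies to Aim 1b by name. The no-loss reading needs near-complete ascertainment, which the plan neither quotes as a rate nor names as the basis for the Aim 1b figure.

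A reader might also infer that 20% incidence is not conservative. The documents do not settle this. The Specific Aims put the rate at 20% or more, the epilepsy outcome text puts it at up to 20%, and the pilot's 15.4% is lower, though small and with follow-up starting at 6 months. At 15.4% the power with both deductions is about 81%. The wording can stay, with power shown across incidence.

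**Conclusion.** The concern holds as a planning-power correction. At 20% incidence, 90:210, 15% loss and 9% inflation, power to exclude 13 points is about 74%, not 80%. The shortfall is about 6 power points; put the other way, 80% power is reached only at 14.2 points, 1.2 above the stated figure. The chance of an inconclusive result under no true difference is 100 − 73.7, about 26%. The result rests on carrying Aim 1a's 9% to Aim 1b and on taking the Missing data section's 15% at its word. With less loss, power rises to at most 79.6% while the inflation is kept.

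Three stronger readings are not supported. That equal allocation was used is an inference from a numerical match. That the limit should become 14 points does not follow: 13 is the only epilepsy figure the decision rule can refer to, so moving it to fit the power would change the analysis. That the conclusions would be invalid is also wrong, since type I error and the observed interval do not depend on planned power. Epilepsy is a secondary outcome.

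**What to change.** Keep 13 points as the limit and do one of the following in the Aim 1b paragraph:

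1. Restate the power as about 74% at 90:210 with 15% loss and 9% inflation, giving the effective N of about 234 (70:164).
2. If near-complete epilepsy ascertainment by record review is the intended basis, say so, justify the expected rate, reconcile it with the 15% loss charged to Aim 1 in the Missing data section, and give power as a range: about 74% at 15% loss to about 80% at no loss, with the 9% inflation.

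In either case, state the effective N, the split, and whether the 9% applies to the epilepsy analysis. Report 14.2 points only as a sensitivity figure. A line showing power at 15.4%, 20% and an assumed 25% incidence would cover the conflicting rates.

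The cost is wording only: no extra infants, and no change to the analysis or conduct.

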For Aim 3, standardized survey results will be compared between the short and prolonged treatment duration groups using parametric and non-parametric bivariate comparison tests as appropriate. Answers to free-text questions will be analyzed using inductive thematic analysis³². This data analysis occurs iteratively and simultaneously with data collection³³. [name] will train the research assistants to undertake coding, and will supervise them through this process. They will engage in repeated close readings of the responses, searching for units of meaning or 'codes' that describe the underlying social processes and interactions. Codes will be organized into categories that are both highly represented in the data and account for the greatest variation in the data³⁵. Open, focused and theoretical codes will then be developed to describe aspects (dimensions) of participants' experiences. Rigor will be maintained through reflexivity, attention to response quality, member reflection and systematic analysis. We will discuss emerging themes with our Parent Partners, to engage in ongoing validation of interpretations and to avoid making assumptions about meaning.

Sensitivity analyses [IR-5]. In order to strengthen causal inference, we will perform a sensitivity analysis using institution as an instrumental variable. Institution is a good instrumental variable: preliminary data from the *Neonatal Seizure* Registry indicate that it is associated with the use of short *versus* prolonged duration of phenobarbital in spite of the fact that patient characteristics (including etiology and seizure frequency) are similar. We have not yet collected data with respect to developmental outcomes for the *Neonatal Seizure Registry*, and so we cannot preclude the impact of institution on outcome; however all important procedures of care that might actually impact outcomes (*e.g.*, therapeutic hypothermia for hypoxic-ischemic encephalopathy) are standardized across the centers for excellence that comprise the *Neonatal Seizure Registry*. As such, we expect the entire effect of institution to be mediated through short versus prolonged treatment with phenobarbital (after adjustment for potential confounders). Since the use of an instrumental variable analysis does not depend on the assumption unmeasured confounders, this instrument will be a good complement to the propensity score matching, which depends on identification of all potential confounders.

Propensity score and instrumental variable analyses may not estimate exactly the same quantity³⁶. A discrepancy between the analyses may point to differences in the average effect of duration of therapy overall (average cause effect or ACE) versus only those who would comply with assignment to short versus long duration (local average treatment effect or LATE). In the situation of a discrepancy between the two analyses, the LATE interpretation of the instrumental variable analysis will still be valuable.

Scales and tests [IR-4].

Primary outcome: The WIDEA FS, a simple, free, one-page assessment to determine functional developmental outcome in children. It will be administered by telephone at age 12-months, 18-months, and 24-months.²⁰ (see **Appendix 3**).

Secondary Outcomes:

- The epilepsy survey to be administered at age 12-months, 18-months, and 24-month has been used in our previous work³. The survey comprises standardized questions and chart review to derive a modified Engel Classification, which is a validated way to describe the severity of epilepsy (see Appendix 4).
- 2) The parent and family well-being assessment will be conducted in conjunction with the hospital discharge and 12-month, 18-month, and 24-month evaluations. Our Parent Partners arrived at consensus on the pertinent domains and selected a suite of validated questionnaires (see **Appendix 5**). They also helped us to design a set of open-ended free-text questions to explore the specific impact of seizure medication on family well-being. These instruments will be available in English and in Spanish.

The NICU discharge survey will have 63 items (answered on a 4 to 5 point scale), a 10 item socio-demographic form, 3 items about the newborn's seizures and treatment plan, and 7 open-ended free text questions. The 12-month survey will have 106 items (answered on a 4 to 5 point scale), a 10 item socio-demographic form and 7 open-ended free text questions to specifically probe the impact of seizure medications on family well-being. The Parent Partners emphasized having choices to complete the surveys online or by mail and so these different options will be made available. They were also mindful that the time to complete the survey packet be no longer than one hour total, with the option to complete the survey packet in several shorter intervals.

Data source adequacy [IR-1]. Data will be collected and entered into a REDCap database according to policies established for the *Neonatal Seizure Registry* discussed below.

Data Accuracy and Editing: The database limits range values for numerical data and will utilize radio buttons or drop down lists rather than free text for qualitative data.

Updating: REDCap automatically creates a historical record of past saved data for each field so that errors can be traced.

Data and Form Checks: Database quality is maintained through analyses that target anomalies, delinquent data, and data entry errors. Along with built-in data validation, the Study Coordinator performs a quarterly check for discrepancies in data that includes: incorrect data types, out-of-range or erroneous data, inconsistent and illogical over-time dates, fields on a "completed form" actually not completed; or no reason for missing data is provided. Sites are notified of data discrepancies and are asked to verify and correct discrepancies within 2 weeks of notification.

Missing data [MD-1 to 5]. The study coordinator will audit the database every 3 months for missing data. In case of missing data, site investigators will be asked to review charts to acquire data and in the case that the data are not available, carefully document in the comments field the reason for missing data.

Based on audits of our *Registry* data, we expect <1% missing data for the following key elements: institution, sex, ethnicity, gestational age at birth, delivery mode, Apgar scores, hypothermia treatment, indication for EEG, seizure type, primary seizure etiology, disposition and seizure medication prescribed at the time of discharge. For Aims 1 and 3, in our study design we have conservatively accounted for 15% loss to follow-up (the anticipated main source of missing data) and have adjusted our enrollment target accordingly. We will perform sensitivity analyses to assess the potential impact of loss to follow-up: we have extensive information about our participants and will compare those that are and are not lost to follow-up. We will compare our primary analysis (a complete case analysis) with an analysis using multiple imputation using the "multiple imputation with chained equations" methodology. This approach allows us to specify realistic models for each variable, such as the ordered categorical for the Engel scale. For Aim 2, we expect little to no missing data. Also, for Aim 3, we will audit the amount of missing data for the open-ended free-text questions to determine if there are patterns and will consult with our Parent Partners about ways to improve response rates if needed.

Heterogeneity of treatment effects [HT-1 to 4]. As suggested by PCORI methodological guidelines, all assessments of heterogeneity of the effect of short versus prolonged phenobarbital treatment have been preplanned and have been justified (see *Potential participant subgroups* section below). Analysis will be by entering subgroup by intervention interaction effects in the analyses described above to test for moderation.

Reporting plan [IR-6]. Data will be reported according to STROBE (Strengthening the Reporting of Observational studies in Epidemiology) guidelines, as is recommended for observational studies.

Patient-centered outcomes research (PCOR) data registry details are presented in Appendix 6.

D. Project Milestones and Timeline

Table 3: Project Timeline

	Months					
	1-6	7-12	13-18	19-24	25-30	31-36
Planning						
- Finalize protocol	\checkmark					
- IRB approval	\checkmark					
 Clinicaltrials.gov registration & results reporting 	~					\checkmark
Patient Enrollment						
- Start recruitment		\checkmark				
- Complete 25% recruitment		\checkmark				
- Complete 50% recruitment			✓			
- Complete 75% recruitment			✓			
- Complete enrollment				~		
Patient Evaluation						
- Follow-up EEG (age 2-4 months) (Aim 1)		✓	\checkmark	\checkmark	\checkmark	
- 24-month follow up (Aim 1) - previous NSR subjects		\checkmark	✓	\checkmark		
- 24-month follow up (Aims 1&3) - newly enrolled subjects			\checkmark	\checkmark	\checkmark	\checkmark
Analysis						
- Interim analysis				\checkmark	✓	
- Final analysis						\checkmark
Progress reports						
- Interim progress reports	\checkmark	\checkmark	✓	\checkmark	\checkmark	
- Final progress report						\checkmark
Engagement Updates	✓	✓	✓	✓	✓	~
Dissemination						
- Write manuscripts					✓	\checkmark
 Submit copies of published manuscripts 					\checkmark	\checkmark
 Presentations by PIs/stakeholders at national meetings 					✓	\checkmark
- Write management guidelines						\checkmark
- Apply for additional funding					✓	\checkmark
- Newsletters to participating families to report results					✓	\checkmark
- Partner with Hand to Hold to disseminate results online					✓	\checkmark

E. Patient Population

Table 4: Quarterly Neonatal Seizure Registry enrollment (6/2013 to 9/2015)			
Site	Median (min, max)	Total Newborns Enrolled in NSR	
UCSF	6 (2, 13)	59	
University of Michigan	12 (5, 16)	102	
MGH	3 (0, 10)	29	

Recruitment Plan. We aim to collect follow-up information for 150 infants that have already been enrolled in the *Neonatal Seizure Registry* (from among >300 eligible newborns; a representative sample of the youngest infants at the time of study initiation will be approached for consent, to allow for prospective collection of 24-

Stanford	6 (0 , 29)	72
СИМС	10 (0, 37)	86
СНВ	11 (5, 17)	79
СНОР	2 (0, 19)	40

month outcome data). An additional prospective sample of 150 newborns will also be enrolled. We have had stable enrollment of 20-30 newborns/month, >70% of whom have acute symptomatic seizures and would meet enrollment criteria for the proposed study. Thus, we expect 250-375 eligible infants over the 18 month enrollment period. We, therefore, will need to enroll 40-60% of eligible newborns, which is very conservative for a non-intervention study with non-invasive follow-up. We will monitor enrollment monthly and address lagging rates on a site-specific basis, as necessary. Given that PCORI requests data within nine months of the end of the final year of funding, even if recruitment is slower than anticipated, there is an additional six months of recruitment time available to us to meet this deadline.

Table 5: Recruitment Goals

	Previously-enrolled	Prospectively-
	infants	enrolled newborns
Total number of study participants expected to be screened:	300	375
Total number of study participants expected to be eligible of	300	300
those screened:		
Target sample size (use same number stated in milestones):	150	150

Race	Male (N) 55%	Female (N) 45%	Total (N)
American Indian/Alaska Native	1	0	1
Asian	10	8	18
Black/African-American	21	17	38
Hawaiian/Pacific Islander	1	0	1
White	88	73	161
Multirace	7	6	13
Ethnicity	Male (N)	Female (N)	Total (N)
Hispanic (Latino/Latina)	25	21	46
Non-Hispanic	112	92	204

 Table 6: Estimated Final Racial/Ethnic and Gender Enrollment Table [RQ-3]

The study population will be newborns with seizures who are admitted at one of the participating children's hospitals, and their parents. Study sites were selected based on their enrollment of patients in the *Neonatal Seizure Registry* and their ability to confirm neonatal seizure diagnoses with video EEG monitoring, according to the American Clinical Neurophysiology Society (ACNS) guidelines³⁷.

Inclusion criteria [RQ-3]

- Neonates <44 weeks postmenstrual age at seizure onset
- Seizures due to an acute symptomatic cause (including, but not limited to hypoxic ischemic encephalopathy, stroke, or cerebral hemorrhage)
- Parent(s) who are English or Spanish literate (with assistance of interpreter)

Exclusion criteria

- Neonates at risk for adverse outcome *independent of* seizures and underlying brain injury (including but not limited to: inborn errors of metabolism, fetal infection, brain malformation, or genetic syndrome)
- Neonates with transient cause for seizures (e.g., mild hypoglycemia, hyponatremia, hypocalcemia)
- Newborns with neonatal-onset epilepsy syndromes

- Neonates who do not survive the initial hospital admission
- Neonates will not be excluded based on race, ethnicity, gender or gestational age

Study population [RQ-3]. We will recruit 300 newborn infants with acute symptomatic seizures (including 150 who were previously enrolled in the *Neonatal Seizure Registry*). No infant will be excluded based on gender, race, or ethnicity. Neonates with seizures are often critically ill, and some do not survive their initial hospital admission (16% in-hospital mortality in the *Neonatal Seizure Registry*). We will only enroll newborns who survive to hospital discharge.

Inclusion of Women & Minorities.

Neonatal seizures affect boys slightly more often than girls (*Neonatal Seizure Registry* data: 55% male, 45% female), but children of all races and ethnicities are affected. Among the *Neonatal Seizure Registry's* subjects, the distribution of race/ethnicity is similar to the American pediatric population. We anticipate a similar distribution for the proposed follow-up study, which will be representative of American children.

Inclusion of Children. All study subjects will be children.

Potential participant subgroups [RQ-4; HT-1 to 4].

Our study is powered to evaluate the primary outcome (development at 24 months) across a wide-ranging population of neonates with seizures. This will improve generalizability. We will also have an opportunity to perform exploratory secondary analyses for some subgroups:

- EEG confirmed vs. clinically diagnosed neonatal seizures: Although all *Neonatal Seizure Registry* sites conform to the ACNS Guidelines for neonatal EEG monitoring³⁸, there are occasions in which an at-risk infant's clinical events resolve prior to the initiation of EEG. In the proper clinical context, many such newborns are treated empirically with anticonvulsant medications. In two small studies, the risk for subsequent epilepsy was higher among infants with EEG-confirmed neonatal seizures than those with clinically diagnosed seizures^{3,39}. Therefore, we will evaluate for differences in 24-month outcomes between those with clinical versus EEG-confirmed seizures.
